6.14.1.4. Implementation Outcomes for the Mobile App

Acceptability of the mobile app to support patients in taking PrEP will be measured by the Acceptability of Intervention Measure (AIM) at months 1, 5, and 11. Appropriateness of the mobile app to support patients in taking PrEP will be measured by the Intervention Appropriateness Measure (IAM) at months 3, 9, and 12.

6.14.1.5. Clinic Staff Acceptability, Appropriateness, and Feasibility of Providing Long-acting Cabotegravir Injections

Acceptability of the process for providing long-acting cabotegravir injections will be assessed by the Acceptability of Intervention Measure (AIM). Appropriateness of the process for providing long-acting cabotegravir injections will be assessed by the Intervention Appropriateness Measure (IAM). Feasibility of long-term use of cabotegravir injections will be assessed by the Feasibility of Intervention Measure (FIM). Willingness to sustain provision of long-acting cabotegravir injections and barriers to and facilitators for provision of long-acting cabotegravir injections will be assessed through a brief survey. The clinic staff surveys will be administered at baseline, month 6, month 12, and end of study.

7. Statistical Analyses

Baseline analyses will include tabulations of demographic and clinical variables of the study participants. Chi-square tests and t-tests will be used to compare these groups to determine if baseline differences exist. The distribution of each continuous variable will be inspected for outliers to determine whether a parametric or non-parametric approach should be applied. The Wilcoxon ranked sum test will be used for any variable that does not meet the statistical assumptions of the t-test. Variables found to be associated with persistence or adherence following univariate analysis will be included in multivariate models.

To assess the co-primary endpoint of persistence at 3 months and end of study, the proportion of participants reporting continued receipt of injections in the CAB-LA cohort and the proportion of patients reporting continued use of PrEP by mouth in the oral PrEP cohort on the persistence assessment will be compared using chi square tests or Fisher's exact tests. Self-reported persistence will be validated by the medication possession ratio (MPR). MPR is defined as the number of days of medication dispensed during the study period divided by the number of days that the person should have received therapy. The percent of CAB-LA participants with MPRs ≥ 1.0 will be compared to the percent of oral PrEP participants with MPRs ≥ 1.0 using chi square tests or Fisher's exact tests. To assess the co-primary endpoint of adherence, chi square tests or Fisher's

exact tests will be used to compare the percent of CAB-LA participants who reported missing one or more injections during the study period to the percent of oral PrEP participants who reported three or more missed days of oral PrEP. The percent of CAB-LA participants who received any injections seven or more days later than their scheduled injection or oral PrEP participants who had a gap of >90 days between the end of the days of supply of a dispensing and the start date of the next fill will be compared.

Sample Size

Assuming adherence proportions of .90 and .65 and sample sizes of 70 and 35 in the CAB-LA and oral PrEP arms respectively, the 95% confidence interval for the difference between the CAB-LA proportion and the oral PrEP proportion is .0771 to .4229.

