2. INTRODUCTION

2.1. Background

2.1.1. Numerous studies have found that medication persistence with oral PrEP (defined as continued use of PrEP over time) tends to be short, with many patients discontinuing oral PrEP within about 6-12 months. Moreover, PrEP persistence has been found to be shorter among underserved populations with health inequities—including Medicaid patients, patients in rural areas, transgender patients, and Black and Latinx patients. The introduction of long-acting, injectable cabotegravir (CAB-LA) for PrEP is viewed by many as an opportunity to overcome adherence

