6.9. PrEP Choice Counselling

6.9.1. Patients will be counseled on the benefits and risks of both oral PrEP and PrEP injections. The selection of PrEP option will be done as the standard of care through shared-decision with the patient.

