6.10. Possible Participant Pathways

6.10.1. There will only be two observational cohort arms. Patients will either be placed into the injectable PrEP arm or the oral PrEP arm based on their baseline prescription.

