Please indicate how much you agree with the following:

	Strongly agree	Agree	Neutral	Disagree	Strongly disagree
4. People experience negative judgment because they take PrEP.	()	()	()	()	()
5. Someone taking PrEP would be seen by others as slutty.	()	()	()	()	()

6. People taking PrEP receive praise for being responsible.	()	()	()	()	()
7. Someone taking PrEP would be treated unfairly by their doctors.	()	()	()	()	()

8. What barriers do you foresee in the implementation of long-acting cabotegravir for PrEP?

[Select up to 2]

- Patient's ability to keep bimonthly appointments
- Patient's transportation for bimonthly appointments
- Flagging/Clinic awareness of missed visits
- Staffing resourcing for clinic flow
- Rescheduling missed injections
- Patients acquiring HIV due to missed dose/visit
- Management of patients with other needs
- Patient injection/soreness

9. Which structural changes or resources may help facilitate long-acting cabotegravir implementation in your clinic? [Select up to 2]

- Increased coordination with other departments (i.e., pharmacy)
- Purchasing new refrigerators
- Finding room space or working around room availability
- Adjusting or extending staff working hours
- Use of different staff for injections
- Making transportation arrangements for patient participants
- Expanding hours for injection visits (i.e., visits in morning or during lunch breaks)
- Accommodating patients needing to reschedule injection visits (i.e. using walk-in visits, same-day appointments)
- Other: [write in]

10. How helpful do you think your clients will find the TheraPay mobile health app in supporting persistence with PrEP?

- Very helpful
- Somewhat helpful
- Neither helpful or unhelpful
- Somewhat unhelpful
- Very unhelpful

11. Do you have a preference for prescribing long-acting cabotegravir or daily oral PrEP?

- Prefer long-acting cabotegravir
- Prefer oral daily PrEP
- No preference

12. How likely is it that your clinic will continue to offer cabotegravir following the completion of this study?

- Very likely
- Somewhat likely
- Neutral
- Somewhat unlikely
- Very unlikely

Thank you for taking the time to complete this survey. Please provide your work email address. Your email will not be tied to your survey responses and will only be used for the purposes of this quality improvement initiative.

- Work email address: [Write in]

THANK YOU FOR COMPLETING THIS SURVEY.

PROVIDER SURVEY (Note: 6 months, 12 months and end of study)

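### Patients and clinicians choose the regimen, yet both co-primary endpoints rest on unadjusted tests, and the planned multivariate models neither name regimen nor rank above those tests

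*Combined protocol and SAP*

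**What the plan says.** The study is an observational cohort (Section 1). On regimen choice, Section 6.9 states: "The selection of PrEP option will be done as the standard of care through shared-decision with the patient". Section 6.10 adds: "Patients will either be placed into the injectable PrEP arm or the oral PrEP arm based on their baseline prescription".

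Section 7 (Statistical Analyses) then sets out three relevant steps.

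- **Co-primary tests.** Persistence at 3 months and end of study: the proportions reported "on the persistence assessment will be compared using chi square tests" or Fisher's exact tests. Adherence follows the same pattern: "To assess the co-primary endpoint of adherence, chi square tests" or Fisher's exact tests. Neither test takes covariates.
- **Baseline comparison.** "Chi-square tests and t-tests will be used to compare these groups to determine if baseline differences exist". No consequence is attached to the result.
- **Models.** "Variables found to be associated with persistence or adherence following univariate analysis will be included in multivariate models". This is the only adjustment language. The sentence gives no model type, time point, regimen term, effect measure or rank against the crude tests.

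The hypothesis (Section 2.3) is worded as an association. The study goal (Section 3.1) is to evaluate how far real-world CAB-LA use impacts adherence and persistence relative to oral PrEP.

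**The concern.** A comparison of self-selected groups answers the Section 3.1 goal only if the groups are alike on what drives persistence, or are made alike by adjustment. The documents give reasons to doubt that they are alike. The Background says "PrEP persistence has been found to be shorter among underserved populations with health inequities", naming Medicaid, rural, transgender, Black and Latinx patients. The staff survey in Appendix D offers "transportation for bimonthly appointments" as a possible barrier to CAB-LA. Factors of this kind could plausibly affect both the choice of regimen and staying on it.

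The documents do not say which arm would hold more such patients, so the crude test could overstate or understate CAB-LA. Two features limit some channelling: patients with a contraindication to either route are excluded (Section 5.2), and West Virginia Medicaid dropped prior authorization for CAB-LA (Section 2.1). Neither addresses channelling through housing, transport, drug use or preference.

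Screening covariates on outcome association can also miss a factor strongly related to regimen when events are few. If crude and adjusted results conflict, the choice between them would be made after the data are seen.

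**Working it through.** **1. The plan's own figure.** Inputs from the Sample Size paragraph: 0.90 of 70 (CAB-LA) and 0.65 of 35 (oral).

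SE = √(0.90×0.10/70 + 0.65×0.35/35) = 0.0882. The 95% CI is 0.25 ± 1.96×0.0882 = 0.077 to 0.423, which matches the stated .0771 to .4229. This interval is for an unadjusted difference and reflects sampling error only.

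**2. Events available for adjustment.** 70×0.10 + 35×0.35 = 7 + 12.25 = 19.25 non-adherent participants. A model can carry only a short covariate list.

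**3. Bias of the crude contrast.** Everything here is assumed: no true regimen effect, 90% persistence without risk factors, 70 versus 35. One factor lowers persistence by 20 points, or three factors lower it by 15 points each. Each factor is present in 30% of one arm and 50% of the other, or in 35% and 45%.

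- Additive effects: bias = number of factors × effect × imbalance. One factor: 0.20×0.20 = 4.0 points. Three factors: 3×0.15×0.20 = 9.0 points. With the imbalance halved: 2.0 and 4.5 points.
- Logistic effects: the odds of persisting with 0, 1, 2 or 3 factors are 9, 3, 1 and 1/3, so persistence is 0.90, 0.75, 0.50 and 0.25. Averaging over independent factors gives 0.741 at 30% prevalence and 0.6125 at 50%, a difference of 12.8 points.

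Rejection by the two-sided 5% chi-square test, 100,000 simulated trials per case:

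| Factors | Imbalance | Effects | Bias (points) | Rejection, bias for CAB-LA / against |
|---|---|---|---|---|
| 1 | 30 vs 50% | additive | ±4.0 | 9.2% / 6.8% |
| 1 | 35 vs 45% | additive | ±2.0 | 6.3% / 5.1% |
| 3 | 30 vs 50% | additive | ±9.0 | 17.6% / 15.8% |
| 3 | 35 vs 45% | additive | ±4.5 | 8.3% / 7.6% |
| 1 | 30 vs 50% | logistic | ±4.0 | 9.0% / 6.8% |
| 1 | 35 vs 45% | logistic | ±2.0 | 6.2% / 5.1% |
| 3 | 30 vs 50% | logistic | ±12.8 | 27.7% / 25.6% |
| 3 | 35 vs 45% | logistic | ±6.4 | 10.7% / 9.9% |

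For scale, the planned interval clears zero by 7.7 points, less than the bias in the two larger three-factor cases. Expected non-persistent participants are 18 to 20 with one factor and 28 to 36 in the 30 vs 50% three-factor cases.

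**4. What adjustment leaves.** Same 16 cases (eight rows, two directions), five binary covariates (the one or three confounders, the rest noise), 6,000 trials each:

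| Analysis | Largest bias (points) | Rejection | CI width relative to crude |
|---|---|---|---|
| Outcome screen p<0.05, regimen forced in | 2.9 | 4.9–6.7% | – |
| Outcome screen p<0.20, regimen forced in | 1.0 | 4.4–5.8% | – |
| Fixed list, linear risk difference, HC3 SE | 0.4 | 4.2–5.3% | 1.00–1.09 |
| Fixed list, logistic, standardised risk difference | 0.3 | 5.5–6.9% | 0.93–1.09 |
| Fixed list, propensity weighting | 0.4 | 4.1–7.8% | 0.99–1.20 |

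The three fixed-list estimators remove the measured bias about equally well, so none is required.

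**The case against.** The strongest reply is that adjustment is already planned. In a two-regimen study, regimen is the natural model term, and on that reading the plan's screened model leaves at most about 3 points. Even read literally, a positive crude test means regimen passes the screen and enters the model. In a separate simulation of that reading (3,000 trials per setting), crude rejection was 7–27%, but crude and adjusted tests both rejected in only 2.7–4.5%. This stands as a limit on the harm. It protects the conclusion only if the adjusted result is allowed to decide, and Section 7 does not say so.

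Other points:

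- **The magnitudes are assumed.** True. The top of the range needs three factors imbalanced by 20 points in the same direction, and implies 32 to 36 events rather than about 19. Rescaled to about 19.6 events, the bias is about 10 points with rejection near 26%.
- **A fixed list gains little over a p<0.20 screen.** True for bias, about half a point. The fixed list's further advantage is that it is settled before outcomes are seen. The plan states no screening threshold.
- **The simulated list is simpler than a real one.** Age is continuous and coverage has several categories. With continuous age, the linear model still left under 0.4 points, with intervals about 6–9% wider than crude and up to 14% wider with nine covariates. The five-covariate linear model also gave fitted values outside 0–1 in 53–80% of datasets, which is a reason to consider the other estimators.
- **The adherence outcomes are unlike.** The plan compares one or more missed injections with three or more missed pill days, the latter from a past-week item (Appendix C). Adjustment does not repair this.
- **The hypothesis speaks only of association.** It does, but the Section 3.1 goal goes further.

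**Conclusion.** The concern holds. As written, the results that decide both co-primary endpoints are crude contrasts of self-selected groups. The one modelling sentence does not guarantee an adjusted regimen effect and does not rank it first.

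The size cannot be known from the documents. In the main illustration it is 2 to 13 points in either direction, with 5–28% false rejection in place of 5%. A single stronger assumed factor (prevalence gaps of 20 to 50 points, effects of 30 to 40 points) gives 6 to 20 points and 12–61%. If the sponsor already intends regimen to be in the screened model and lets that model decide, the remaining bias is about 3 points or less, and the defect is mainly one of specification.

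These results assume that the confounders are measured and in the model. Rural residence, named in the Background, is not in the baseline survey. The event count of about 19 comes from the adherence planning rates. No persistence rate is given, so events at month 3 could be fewer.

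**What to change.** Amend Section 7 for three contrasts: persistence at month 3, persistence at end of study, and the missed-dose adherence comparison.

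1. Make the primary result an adjusted regimen difference with 95% CI, from one pre-specified analysis with regimen always included.
2. Replace the outcome-based screen with a short fixed list of month 0 items asked identically in both arms (Appendices B and C). Age, health coverage, housing instability, transport barrier and past-30-day drug use are one example. Gender and race/ethnicity are also collected and may be swapped in, given the groups named in the Background. Keep the list to about five because of the expected event count.
3. Keep the chi-square or Fisher tests as unadjusted supportive results.
4. Report standardised differences between arms at baseline.
5. Fix the estimator (regression-based risk difference or propensity weighting), the covariate coding and the rule for missing baseline answers before outcomes are seen. The choice is the sponsor's.

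The cost is SAP wording and modest analysis work, with no new data. With five binary covariates, intervals were at most 9% wider than crude by regression and 20% wider by weighting. The change does not address unmeasured confounding or the differing adherence definitions, and both should be stated as limitations.

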6.2.3. Persistence Assessment CAB-LA

6.2.3.1. The proportion of participants who received at least one PrEP injection who remained on injectable PrEP or oral bridging at months 3 and 11 measured by the self-report assessment and validated with claims data.

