6.2.4. Persistence Assessment Oral PrEP

6.2.4.1. The proportion of participants who initiated oral PrEP who remained on oral PrEP at months 3 and 12 measured by the self-report assessment and validated with claims data period.

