6.14. STATISTICAL ANALYSIS

6.14.1. Study Endpoints

6.14.1.1. Medication Adherence and Persistence

Medication persistence is defined as continuing to take PrEP over time independent of adherence to the medication regimen. The proportion of

patients reporting receipt of CAB-LA or oral PrEP at months 3 (early) and end of study (late) will be measured through patient questionnaires and validation protocols. Medication adherence is defined as taking PrEP in line with medical advice.

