13.1.5. Incentive Mapping

13.1.6. List of Tables

13.1.6.1. Study Procedures

13.1.7. List of Figures

13.1.7.1. Study Schema

13.1.7.2. Study Timelines

13.1.8. Forms for Safety Reporting

1. PROTOCOL SUMMARY

Title	A Transformative Approach Utilizing Behavioral Economics, Education, and Data Science to Support Patients Initiating PrEP with Retention-in-care and Medication Persistence
Funder	ViiV Healthcare
Study Design	Observational Cohort Study
Study Population	Patients >18 y/o who are newly started on PrEP at WVHR and have access to a smart phone with data.
Study Size	n = 105 (70 CAB-LA intervention participants and 35 oral PrEP participants)
Study Duration	12 months
Study Site(s)	West Virginia Health Right
Intervention Description	Participants will have been prescribed CAB-LA, daily FTC/TDF, or daily FTC/TAF in accordance with the WVHR standard of care by a licensed HCP prior to enrolling in the study. Those receiving CAB-LA will be in one arm and those receiving oral therapy will be in the other arm of the study.
Study Aim	To determine the persistence in injectable PrEP compared to Oral PrEP therapy
Primary Objectives	To evaluate medication persistence in patients receiving CAB-LA vs oral PrEP and who engage with a digital health companion program
Secondary Objective 1	Evaluate Retention-in-care in patients receiving CAB-LA vs oral PrEP
Secondary Objective 2	Evaluate PROs (including PrEP medication satisfaction, PrEP acceptance, stigma, and reasons for PrEP discontinuation) in patients receiving CAB-LA vs oral PrEP
Secondary Objective 3	Evaluate the acceptability, appropriateness, and helpfulness of a digital health companion program for PrEP

Secondary Objective 4	Evaluate the acceptability, barriers to, and facilitators for implementation of CAB-LA
--------------------------	--

Study Schema Figure

Figure showing study components and flow – organize by participant cohort (i.e. oral, LA, no PrEP)

Study Outcomes Table

Primary or Secondary Endpoint	Definitions	Type of Endpoint	Assessment Timepoint	Data Source	Intervention or Approach	Tool/Instrument for Endpoint
1. Primary Endpoint: PrEP adherence and Persistence	Proportion of patients reporting receipt of CAB-LA injections or use of oral PrEP at 3 months after PrEP initiation and end of study	Quantitative	M3 and end of study	Participant survey and EHR	Participant survey and EHR	Survey and Medication Retention Ratio

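### Self-reported persistence is called validated by MPR, but the only MPR analysis stated is a between-arm test over the whole study period; no participant's answer is set against that participant's own record

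*Combined protocol and SAP*

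**What the plan says.** Section 7 compares the arms on self-reported persistence at two time points: "To assess the co-primary endpoint of persistence at 3 months and end of study, the proportion of participants reporting continued receipt of injections". This CAB-LA proportion is tested against the corresponding oral proportion by chi-square or Fisher's exact test. It continues: "Self-reported persistence will be validated by the medication possession ratio (MPR". The measure covers the whole study: "MPR is defined as the number of days of medication dispensed during the study period divided by the number of days" of therapy due. One MPR analysis follows, by the same two tests: "The percent of CAB-LA participants with MPRs ≥ 1.0 will be compared to the percent of oral PrEP participants with MPRs ≥ 1.0".

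Other places promise a check against records without giving a method:

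- Section 6.2.3 (CAB-LA) says persistence is "measured by the self-report assessment and validated with claims data", and Section 6.2.4 (oral) says much the same.
- Section 6.14.1.1 says persistence "will be measured through patient questionnaires and validation protocols", and describes no such protocol.
- The Study Outcomes Table names the tool as "Survey and Medication Retention Ratio", a different term.
- The schema in Appendix G describes the ratio as a quantity between the two cohorts.

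Section 6.2.2 defines persistence as continuing PrEP irrespective of adherence.

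**The concern.** To validate a self-report is to ask whether the people who say they are still on PrEP are shown to be on it by their own records, at the time they answered. The plan states two parallel arm comparisons on two different variables, and no step joins the two sources within a participant. It gives no agreement measure, no over-report or under-report rate, and no rule for discordant cases.

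This matters because the co-primary persistence endpoint is self-report and the question differs by arm. CAB-LA participants are asked about injections the clinic gives; oral participants are asked about pills they take themselves. Misreporting could therefore differ by arm, by an amount and in a direction the documents do not tell us. A report that followed Section 7 could call the endpoint validated without showing how accurate the answers were. If agreement and discordance rules are chosen after the results are seen, the choice between self-report and records becomes post hoc.

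**Working it through.** **1. The plan's own figure.** Section 7 (Sample Size) assumes .90 of 70 and .65 of 35.

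SE = √(.90×.10/70 + .65×.35/35) = √(.001286 + .006500) = .08824.

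95% CI = .25 ± 1.96×.08824 = .0771 to .4229.

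This matches the stated interval. The point does not depend on it.

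**2. What the stated analyses use.**

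| Analysis in Section 7 | Variable | Time | Comparison |
|---|---|---|---|
| Persistence | self-report | month 3, end of study | CAB-LA vs oral |
| MPR | MPR ≥ 1.0 | whole study period | CAB-LA vs oral |

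Neither row pairs the two variables within a participant, and no other section supplies the pairing.

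**3. Does MPR ≥ 1.0 measure the same thing?** Each participant has one whole-period MPR but two persistence statuses. Someone on PrEP at month 3 and off it at the end has two different answers and one ratio. The cut-off also demands full possession: one uncovered day in 365 gives 364/365 = 0.997, which fails although the person is still persistent under Section 6.2.2.

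**4. What arm percentages can show.** Let s be the proportion persistent by report and r the proportion persistent by record. The error that self-report brings into the arm difference is

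(s₁ − s₂) − (r₁ − r₂) = (s₁ − r₁) − (s₂ − r₂),

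which is net over-reporting in CAB-LA minus net over-reporting in oral PrEP. It needs arm totals only, but r must be on-PrEP status at the same time point. If net over-reporting were anywhere from 0 to 15 points in each arm (an assumed range), the error would lie between −15 and +15 points.

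Whole-period MPR ≥ 1.0 cannot stand in for r. Assume every self-report is correct, 63/70 and 23/35 are persistent, and 13 persistent participants in each arm have one uncovered day. MPR ≥ 1.0 is then 50/70 and 10/35. Report minus MPR is 13/70 = 18.6 points in CAB-LA and 13/35 = 37.1 points in oral PrEP. That looks like heavy, unequal over-reporting when there is none.

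**5. What arm percentages cannot show.** Assume both sources give 63/70 in CAB-LA and 23/35 in oral PrEP, close to .90 and .65. With n participants and m positive by each source, the number positive on both lies between max(0, 2m − n) and m. Lower limits:

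- CAB-LA: 56 positive on both and none negative on both. Agreement is 56/70 = 80.0%. Chance agreement is (63² + 7²)/70² = .820, so kappa = (.800 − .820)/.180 = −0.11. Reports supported by the record: 56/63 = 88.9%.
- Oral: 11 positive on both and none negative on both. Agreement is 11/35 = 31.4%. Chance agreement is (23² + 12²)/35² = .549, so kappa = (.314 − .549)/.451 = −0.52. Reports supported by the record: 11/23 = 47.8%.

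The upper limits are 100% and kappa 1.00 in both arms. The between-arm result is the same at either end.

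**6. Precision of a participant-level check.** The Wald half-width is 1.96×√(p(1 − p)/n), taking true agreement p as 70% to 90% (assumed) with every participant contributing. For n = 35 it is 15.2 to 9.9 points; for n = 70 it is 10.7 to 7.0 points.

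**The case against.** The strongest reply is that the method is unspecified rather than wrong. In Section 7 the validation sentence stands apart from the sentence on the between-arm test, and the plan never says that the test is the validation. Sections 6.2.3, 6.2.4 and 6.14.1.1 and the Study Outcomes Table all signal an intention to check self-report against records. That stands. A reader might infer that no validation is intended or will take place; the documents do not support that. They show only that no validating analysis is written down.

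A reader might also infer that the plan could never detect unequal over-reporting. That is too strong. As step 4 shows, with a record measure of on-PrEP status at the right times, net over-reporting by arm could be read from the arm percentages. The obstacle is the whole-period MPR ≥ 1.0 measure. Likewise, the agreement limits in step 5 describe individual misclassification. In that illustration, net over-reporting is zero in both arms at every value of kappa, so the limits say nothing about bias in the arm difference.

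Finally, dispensing records show possession, not ingestion, so no cross-table will reveal pills collected but not taken. That also stands and limits what the fix can claim.

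**Conclusion.** The point holds in a limited form. As written, Section 7 would describe a co-primary self-report endpoint as validated on the strength of a between-arm test that neither pairs answers with records nor measures on-PrEP status at month 3 or end of study.

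The size of any resulting bias cannot be derived from the documents: they give no misreporting rates, and its direction is open. What can be shown is that the stated test leaves individual agreement undetermined (80.0% to 100% in CAB-LA and 31.4% to 100% in oral PrEP, assuming equal totals from both sources), and that MPR ≥ 1.0 can differ from self-report when every answer is true. A reader might conclude that the persistence comparison itself is invalid. The documents do not support that: the comparison is fully specified without the validation step, and the primary test, sample size and stated interval are untouched. This is a should-fix.

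**What to change.** Replace the validation sentence in Section 7 with a participant-level analysis:

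- Within each arm, at month 3 and end of study (month 11 for CAB-LA and month 12 for oral, per Sections 6.2.3 and 6.2.4), cross-tabulate self-report against on-PrEP status from injection or dispensing records. This makes four tables.
- Derive record status from a coverage definition that the sponsor fixes before analysis. It should say how an injection or fill converts to covered time, and how oral bridging is classified, since Section 6.2.3 counts it as persistence. State how discordant and missing cases are handled.
- Report percent agreement and over-report and under-report rates, with 95% CIs, by arm.
- Repeat the between-arm persistence comparison on record status as a sensitivity analysis.
- Keep the MPR ≥ 1.0 comparison as a separate descriptive result, not called validation, and use one name for the ratio throughout.
- State that dispensing records confirm possession, not ingestion, and that estimates from 35 oral participants will be imprecise.

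The cost is SAP wording, a coverage rule and a little more analysis. No new data collection appears to be needed: Section 5.1.3 requires dispensing by the site pharmacy, the Study Outcomes Table lists the EHR as a source, and the late-injection and refill-gap measures in Sections 6.2.6 and 6.2.7 already need dated records. The downside is that self-report may prove less accurate than hoped.
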